3.3.4 Patient Inclusion Criteria

For enrollment into the study, patients are required to meet the following inclusion criteria:

Table 3.3.4-1 Inclusion Criteria	
1.	Patients are actively enrolled in an Anthem-affiliated commercial, Medicaid, or Medicare health plan with medical and pharmacy benefits.
2.	Male and female patients between the ages of 18 and 63 years, inclusive at the time of consent.
3.	Patients must have a smartphone with data plan.
4.	Patients must have a current diagnosis of SCH, BP1, or MDD.
5.	Patients currently prescribed aripiprazole, or appropriate for aripiprazole treatment.
6.	Within 60 days prior to study enrollment, patients are required to have had a hospitalization (all cause or psychiatric) or at least 1 psychiatric partial hospital admission.
7.	Patients are deemed appropriate, per the study physician judgment, to use Abilify MyCite per the package insert and to enter this interventional study.
8.	Patients must be able to read and understand English.

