3.3.5 Patient Exclusion Criteria

For enrollment into the study, patients will be excluded if they fall under any of the following exclusion criteria.

Table 3.3.5-1 Exclusion Criteria	
1.	Any patient who participated in another clinical trial within 30 days of enrollment into the current study.
2.	Females who are breast-feeding and/or who are pregnant at the time of study enrollment, or who plan to become pregnant during the study.
3.	Patients who are currently being treated with a long-acting injectable antipsychotic.

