3.6.3 Individual Patient

Patient withdrawal from the study will be based upon physician clinical determination and/or patient decision. Participation in the study is voluntary, and all patients are free to terminate their participation at any time. In the event of study withdrawal, the study physician will record the reason for study withdrawal and continue to follow-up with the patient for any unresolved SAEs. Upon patient withdrawal from the study, all data collection will end, but all study data collected up to withdrawal will be included in the study database.

In addition, patients falling under the following criteria must be withdrawn from the study:

- occurrence of any intercurrent illness or abnormality in a laboratory assessment which, in the opinion of the physician, warrants the patient's permanent withdrawal from the study;
- at the request of the patient or physician;
- patient becomes pregnant; or
- patient is lost to follow-up.

3.6.4

CCI

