4.5 Pregnancy

Females of childbearing potential (FOCBP) are defined as female patients or female partners of the male patients for whom menstruation has started and who are not documented as sterile (eg, have had a bilateral oophorectomy and/or hysterectomy or who have been postmenopausal for at least 12 months).

Before study enrollment, FOCBP must be advised of the importance of avoiding pregnancy during study participation and the potential risk factors for an unintentional pregnancy. The patient must sign an ICF stating that the risks and consequences were discussed with her.

During the study, all FOCBP should be instructed to contact the HCP immediately if they suspect they might be pregnant (eg, missed or late menstrual cycle).

If a female patient is suspected to be pregnant before the patient receives Abilify MyCite, the investigator can recommend the patient undergo a pregnancy test with their general practitioner or primary care physician. If the pregnancy is confirmed, the patient must not receive Abilify MyCite and must not be enrolled in the study. If pregnancy is suspected while the patient is taking Abilify MyCite, Abilify MyCite may be continued at HCP discretion until the result of the pregnancy test is known. If pregnancy is confirmed, Abilify MyCite may be continued at HCP discretion based on treatment guidelines for the medication administered. If the HCP discontinues the patient from Abilify MyCite, it must be performed in an appropriate manner (eg, dose tapering if necessary for patient safety) and the patient will be withdrawn from the study. (Exceptions to study discontinuation may be considered for life-threatening conditions only after consultations with the Clinical Safety and Pharmacovigilance department [see the cover page of this protocol for contact information]).

The HCP must immediately notify the sponsor of any pregnancy associated with Abilify MyCite exposure during the study and for 30 days for a female patient, 90 days for female partner of a male patient, after the last dose of Abilify MyCite, and record the event on the IRE form and forward it to the sponsor. Pregnancies of patients or their partners will be followed to term. In the event of pregnancy of a patient's partner, consent to follow the pregnancy will be obtained. The sponsor will forward Pregnancy Surveillance Form(s) for monitoring the outcome of the pregnancy.

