3.4 Virtual Matched Control Group

Enrolled patients will be matched to a virtual control group in a 1:3 ratio (enrolled patients on Abilify MyCite treatment : virtual matched controls). [REDACTED]

The matching process will be conducted after 6-month study data (or early termination data, if applicable) is collected for all Abilify MyCite patients. The virtual matched control group identified in this process will be used for all study analyses with a small amount of attrition expected for the 12-month analyses for controls who no longer have Anthem insurance coverage.

A pool of potential controls will first be identified using the following criteria:

- ≥ 1 day of enrollment in an Anthem-affiliated commercial, Medicaid, or Medicare health plan with medical and pharmacy benefits during the observation period (from date of First Patient In up until date of Last Patient In)¹³.
- ≥ 1 pharmacy claim for any atypical antipsychotic (excluding Abilify MyCite, clozapine, and long-acting injectable antipsychotics [LAIs]^{14,15}) during the observation period (Appendix F, Tables 2a and 2b).

¹³ Timeframe may be extended if additional samples are needed.

¹⁴ LAIs include: Aripiprazole monohydrate (Abilify Mantenna), Aripiprazole lauroxil (Aristada), Olanzapine pamoate (Zyprexa Relprevv), Paliperidone palmitate (Invega Sustenna), Paliperidone palmitate (Invega Tri state), Risperidone microspheres (Risperdal Consta)

¹⁵ Drugs include: Aripiprazole, Asenapine, Brexpiprazole, Cariprazine, Iloperidone, Paliperidone, Pimavanserin tartrate, Quetiapine fumarate, Risperidone, Ziprasidone, Ziprasidone Mesylate

- ≥ 1 all-cause hospitalization or partial psychiatric hospitalization¹⁶ that occurs at most 60 days prior to a pharmacy claim for any atypical antipsychotic (excluding Abilify MyCite, clozapine, and LAIs).
 - The earliest such pharmacy claim observed after the earliest observed hospitalization will be set as the initial (temporary) index date for each potential control.
 - For patients with ≥ 2 qualifying hospitalization/pharmacy claim episodes, an iterative process will be used to find the best match, and the final index date will be assigned accordingly.
- Age 18 to 63 on index date.
- ≥ 1 claim for SCH, BP1, or MDD on or before index date.
- No claims for pregnancy during the observation period.
- No claims for any LAI during the observation period.
- ≥ 180 days of medical and pharmacy enrollment prior to index date

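### The pregnancy exclusion is timed at enrollment for Abilify MyCite patients but over the whole First-to-Last-Patient-In window for controls, so an in-window delivery can qualify a patient for one arm and bar her from the other

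*SAP*

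**What the plan says.** **Abilify MyCite arm.** Protocol 3.3.5, exclusion 2, keeps out "Females who are breast-feeding and/or who are pregnant at the time of study enrollment, or who plan to become pregnant during the study". SAP 3.2 adopts the protocol criteria. The qualifying event in Protocol 3.3.4 is that, within 60 days before enrollment, "patients are required to have had a hospitalization (all cause or psychiatric) or at least 1 psychiatric partial hospital admission". No text excepts a delivery admission.

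**Control pool.** SAP 3.4 also accepts any all-cause hospitalization, provided it is one "that occurs at most 60 days prior to a pharmacy claim for any atypical antipsychotic" (other than the excluded products). It then adds the condition "No claims for pregnancy during the observation period". That period is calendar time: "during the observation period (from date of First Patient In up until date of Last Patient In", and a footnote lets the timeframe be extended. The index date is set separately for each potential control.

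**Pregnancy after baseline, Abilify MyCite arm.** Protocol 3.6.3 lists "patient becomes pregnant; or" among the criteria for mandatory withdrawal and ends data collection at withdrawal. Protocol 4.1.4 says pregnancy mandates discontinuation of Abilify MyCite. Protocol 4.5 says "If pregnancy is confirmed, Abilify MyCite may be continued at HCP discretion based on treatment guidelines for the medication administered". SAP 5.1.2 limits the analysis population to patients who completed a Day 180 visit.

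**The concern.** The comparison is not randomized, so it relies on both arms being drawn by the same eligibility rules. Here one exclusion has two definitions.

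For an Abilify MyCite patient, the test is her state on one day. For a control, it is the absence of any pregnancy claim over the whole enrollment window, whether before, at or after her index date. This has two consequences.

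- **Different women are admitted.** A delivery in the window can be the admission that qualifies an Abilify MyCite patient, while the same admission is a pregnancy claim that removes a control.
- **Controls are selected on their future.** A control indexed early is screened on claims well after index, possibly beyond her 180 days. One indexed near Last Patient In is hardly screened after index. Because the endpoint is all-cause hospitalization, some of the post-index claims that remove a control may themselves be endpoint events.

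The quantity at stake is P1 - P2, for which the plan assumes a difference of 7.26 points.

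**Working it through.** **1. Can the same woman be eligible in one arm only?** Take a woman with MDD, BP1 or SCH who delivered in hospital 40 days ago, inside the window, is not breast-feeding and plans no pregnancy.

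| Rule | Abilify MyCite arm | Control pool |
|---|---|---|
| Any-cause admission within 60 days | met | met, if an antipsychotic claim follows in time |
| Pregnancy rule | not excluded: not pregnant at enrollment | excluded: the delivery is a claim in the window |

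There are two limits. The breast-feeding exclusion keeps some recently delivered women out of the Abilify MyCite arm. A delivery just before First Patient In is not itself an in-window claim.

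**2. The plan's own figure.** Inputs from SAP 4.2 are 29.04% versus 36.30%, ratio 1:3, 80% power and 0.025 one-sided. The stated unpooled formula gives

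n = (1.960 + 0.842)² × [0.2904×0.7096 + 0.3630×0.6370/3] / 0.0726² = 7.849 × 0.28314 / 0.005271 ≈ 422.

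With pooled variance under the null it is 441, within 3% of the stated 447. Also 447/0.7 = 639 (stated 640), and 3 × 447 = 1,341 (stated about 1,350). The 447 is used below only to set the standard error.

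**3. Standard error with no true effect.** SE = √[0.363×0.637×(1/447 + 1/1,341)] = 2.63 points.

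**4. Delivery-qualified patients in the Abilify MyCite arm only.** Let f be their share and r their 180-day rate. Both are assumptions. All other patients are at 36.3%.

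Shift towards Abilify MyCite = f × (36.3% - r). One-sided error = Φ(shift/SE - 1.96).

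| f | r | Shift (points) | Share of 7.26 | One-sided error |
|---|---|---|---|---|
| 1% | 10% | 0.26 | 4% | 3.1% |
| 3% | 10% | 0.79 | 11% | 4.9% |
| 5% | 10% | 1.3 | 18% | 7.2% |
| 5% | 5% | 1.6 | 22% | 8.6% |
| 5% | 20% | 0.8 | 11% | 5.0% |
| any | 36.3% | 0 | 0 | 2.5% |

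If r exceeds 36.3%, the sign reverses.

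**5. Controls deleted for obstetric admissions during follow-up.** If a share g of controls has such an admission, and so an event, deleting them changes P2 to (0.363 - g)/(1 - g).

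- g = 1%: 35.7%, a fall of 0.6 points.
- g = 2%: 35.0%, a fall of 1.3 points.

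This works against Abilify MyCite and is as large as the shifts in step 4. It is not all asymmetry. Controls already pregnant at index correspond to patients whom exclusion 2 keeps out. Controls who become pregnant later correspond to patients who may be withdrawn under Protocol 3.6.3 and then lost to the Day 180 completer population.

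**6. Pregnancies first claimed after Last Patient In.** These controls stay, and their obstetric admissions count as events, while a patient withdrawn for pregnancy is not analysed. This effect favours Abilify MyCite, the same direction as step 4 when r is below 36.3%.

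**The case against.** **The size is assumed throughout.** This stands. No text gives a delivery share, nor says that women with these diagnoses are rehospitalized less often after a delivery. A 5% share may be high for a mixed-sex sample aged 18 to 63 with breast-feeding women excluded. Step 4 is an illustration only.

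**The bias has no fixed direction.** This also stands. A reader might infer that the rule favours Abilify MyCite and raises the type I error. The documents do not support that as a net claim, because step 5 runs the other way at a similar size.

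**The balance check would catch it.** SAP 3.4 requires an overlap plot and standardized differences with a 10% flag before outcomes are assessed. If delivery were tabulated, shares of 1%, 3% and 5% against 0% give f/√[f(1-f)/2] = 14%, 25% and 32%, all flagged. But type of qualifying admission is not among the visible covariates. Comorbidities is open-ended and one list item is redacted, so it could be included. Even then, a flag cannot supply controls whom the pool definition has removed, and regression has none to estimate from.

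**The control rule roughly parallels withdrawal for pregnancy.** Partly so, for pregnancies arising after baseline. It follows that barring post-index claims for controls alone would open a new gap unless the withdrawal and completer rules are addressed too. It does not help with deliveries before index.

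**Conclusion.** The mismatch is established from the text alone. The two arms apply the pregnancy exclusion at different times, an in-window delivery can qualify a patient for one arm and bar her from the other, and control selection uses post-index claims that may be outcomes. How far forward the control rule looks depends on when in the window she was indexed.

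The net size and direction are not established. With an assumed 10% rate and shares of 1% to 5%, the delivery effect alone is 0.3 to 1.3 points towards Abilify MyCite, with a one-sided error of about 3.1% to 7.2%. Deletion of controls with obstetric admissions offsets this by an unknown amount, illustrated at 0.6 to 1.3 points.

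A reader might also take withdrawal on pregnancy as settled. It is not: Protocol 3.6.3, 4.1.4 and 4.5 disagree.

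SAP 5.0 records that the study stopped after two patients with no efficacy assessment, so this concerns the plan and no result. The point is worth correcting because the remedy is cheap and like-for-like eligibility is the basis of the comparison.

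**What to change.** 1. Replace the SAP 3.4 bullet with a rule anchored to the index date: exclude a potential control whose pregnancy is ongoing at index, judged from claims up to index with no delivery or other end of pregnancy before it. Planned pregnancy cannot be read from claims; state this as a remaining difference.
2. For the primary comparison, remove patients whose qualifying admission was a delivery from both arms, using one claims definition. Among these women this also avoids the breast-feeding mismatch, since claims are not a reliable record of breast-feeding. An index rule on its own would admit breast-feeding controls while the protocol excludes such patients.
3. Write one analysis rule for pregnancies arising in Days 1-180 and apply it identically to both arms. It replaces the calendar-window claim exclusion for controls and the withdrawal plus completer exclusion for Abilify MyCite patients. It must be workable given that Protocol 3.6.3 ends data collection at withdrawal.
4. Reconcile Protocol 3.6.3, 4.1.4 and 4.5 on what follows a confirmed pregnancy.

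The cost is SAP wording, claims programming, and a few Abilify MyCite patients leaving the primary comparison. The sample size formula is unaffected.

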3.5.1.5 Main Study: Treatments

Patients will initiate Abilify MyCite upon study enrollment (at the baseline visit) and will continue use through Day 90 (with an optional second use period over Days 180-≤360),

as deemed clinically appropriate by their treating physician. Abilify MyCite may be started and stopped as clinically appropriate based on physician judgment. Ability MyCite metrics will be captured throughout use.

During periods of nonuse of Abilify MyCite, the patient continues with oral aripiprazole or other appropriate treatment, per routine clinical care.

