- ≥ 180 days of medical and pharmacy enrollment following index date

Prior to matching, the pool of potential controls and the Abilify MyCite cohort will be stratified by psychiatric diagnosis (SCH, BP1, MDD). The Abilify MyCite cohort psychiatric diagnosis will be based on the psychiatric diagnosis recorded in the eCRF. The potential controls psychiatric diagnosis will be based on the psychiatric diagnosis identified [REDACTED] CCI. In the event that more than one of the qualifying psychiatric diagnoses is identified [REDACTED] CCI, the following hierarchy will be applied to potential controls: SCH>BP1>MDD.

From this pool of patients, combined with the active arm, logistic regression will be used within each psychiatric diagnosis to estimate a propensity score for each patient, where propensity refers to a patient's pre-index likelihood to be in the active arm. The dependent variable equals 1 for patients in the active arm and 0 for the controls. The following variables may be considered for inclusion in the propensity score model; a final determination will be made using descriptive study results on patient baseline characteristics.

- Age
- Gender
- Month of index date
- Plan type (commercial, Medicaid, or Medicare health plan with medical and pharmacy benefits)
- Number of fills for any atypical antipsychotic over 6-12 months prior to index date
- [REDACTED] CCI
- Occurrence/number of visits with a psychiatrist over 6-12 months prior to index date
- Comorbidities over 6-12 months prior to index date

¹⁶ Defined as a medical claim with place of service code = 52 ("Psychiatric Hospitalization"), or with HCPCS codes H0035 or S0201.

- Region of patient residence (Northeast, South, Midwest, West)

The estimated propensity scores will be used to match active arm patients to the virtual controls in a 1:3 ratio. Prior to assessing outcomes, the validity of the propensity score adjustment will be assessed by (1) graphically examining the overlap in propensity scores across treatment and control groups¹⁷, and (2) comparing balance in all baseline characteristics across the cohorts via standardized mean differences. A standardized mean difference >10% in absolute value will be used to indicate potential imbalance that may warrant further investigation or adjustment (e.g. through regression analysis).¹⁸ Propensity score models will be finalized prior to the assessment of outcomes.

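### Controls are excluded for LAI claims in a calendar window that can run past their index date, with no stated equivalent in the MyCite arm; four Abilify Maintena codes are also listed as non-LAI

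*SAP*

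**What the plan says.** **Controls.** Among the conditions for the control pool, SAP 3.4 requires "No claims for any LAI during the observation period". The same list defines the window as the "observation period (from date of First Patient In up until date of Last Patient In", and footnote 13 adds: "Timeframe may be extended if additional samples are needed". A control's index date is a qualifying antipsychotic pharmacy claim after a hospitalization. Age, diagnosis and enrollment in this list are all anchored to the index date, including at least "180 days of medical and pharmacy enrollment prior to index date". The LAI rule is not.

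**MyCite patients.** Protocol 3.3.5 excludes "Patients who are currently being treated with a long-acting injectable antipsychotic", judged at entry. Afterwards, in periods without MyCite, Protocol 3.5.1.5 says "the patient continues with oral aripiprazole or other appropriate treatment, per routine clinical care". Starting an LAI is not among the withdrawal criteria in Protocol 3.6.3. The analysis population in SAP 5.1.2 depends on eligibility and a Day 180 visit, with no LAI condition after baseline.

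**Matching.** SAP 3.4 defines propensity as a patient's "pre-index likelihood to be in the active arm".

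**Code lists.** Footnote 14 to SAP 3.4 begins "LAIs include: Aripiprazole monohydrate (Abilify Mantenna" (evidently Abilify Maintena), so the product is classed as an LAI. Appendix F, Table 2b (LAI) gives two codes for it. Table 2a (non-LAI) gives four others.

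**The concern.** The control screen should reproduce the entry rule for MyCite patients: no LAI at the start of follow-up. As written it does something else.

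- For any control indexed before Last Patient In, it looks at claims made after index, inside the outcome period.
- For a control indexed early in the window, the visible text searches little or no time before index, although 180 days of prior enrollment are required. The rule can miss LAI use at entry while screening on later use.

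Under SAP 3.1, treatment as usual in the control group is any product other than MyCite, so a later move to an LAI is part of the comparator. Removing those controls while keeping MyCite patients who make the same move conditions one arm on its future. A control dropped this way never enters the pool, so neither the propensity score nor the baseline balance checks would show it.

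The control hospitalization rate in the primary comparison is at stake. If the removed controls are at lower risk than the rest, that rate rises and false positives for MyCite increase. If they are at higher risk, it falls and power is lost. The comparison is not randomized, and nothing planned would detect either.

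**Working it through.** **1. Reach of the screen.** The share of a control's outcome period inside the LAI window is min(D, 180)/180, where D is the number of days from index to Last Patient In.

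- D = 0: 0%
- D = 30: 30/180 = 17%
- D = 90: 90/180 = 50%
- D = 180 or more: 100%

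This needs no assumption about how index dates are spread. Footnote 13 does not say in which direction the window may be extended; only a later end date would lengthen the post-index screen.

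**2. Base case.** Inputs from SAP 4.2: p1 = 0.2904, p2 = 0.363, n = 447 MyCite patients, 3 × 447 = 1,341 controls, one-sided level 0.025, Z-test with unpooled variance.

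- SE = √(0.2904 × 0.7096/447 + 0.363 × 0.637/1,341) = 0.02517
- Power = Φ(0.0726/0.02517 − 1.96) = Φ(0.925) = 82.2%

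The plan states 80%. That gap is a separate matter; 82.2% serves here as the reference. Setting p1 = 0.363 gives a type I error of 2.50%.

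**3. Illustration of the effect.** Two quantities are assumed because the documents do not give them: f, the share of controls removed for a post-index LAI claim, and g, the 180-day hospitalization risk of those removed. The 36.3% is taken as the rate before removal; its source is redacted.

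Remaining control rate = (0.363 − f·g)/(1 − f). Power and type I error follow from the formula in step 2, with p1 = 0.2904 and p1 = 0.363 respectively.

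| f | g | Control rate | Power | One-sided type I error |
|---|---|---|---|---|
| any | 36.3% | 36.30% | 82.2% | 2.50% |
| 1% | 25% | 36.41% | 83.4% | 2.8% |
| 1% | 60% | 36.06% | 79.7% | 2.0% |
| 2% | 25% | 36.53% | 84.5% | 3.1% |
| 2% | 60% | 35.82% | 76.9% | 1.6% |
| 5% | 25% | 36.89% | 87.7% | 4.15% |
| 5% | 45% | 35.84% | 77.2% | 1.6% |
| 5% | 60% | 35.05% | 66.8% | 0.7% |

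Worked rows:
- f = 5%, g = 25%: rate (0.363 − 0.0125)/0.95 = 0.3689; type I error Φ(0.00595/0.02629 − 1.96) = Φ(−1.734) = 4.15%.
- f = 5%, g = 60%: rate (0.363 − 0.030)/0.95 = 0.3505; power Φ(0.0601/0.02512 − 1.96) = Φ(0.434) = 66.8%.

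**4. Check with the test named in SAP 4.4.** For McNemar's test, power = Φ((d − 1.96√(s/n))/√((s − d²)/n)), with d the difference and s the sum of the discordant proportions. Taking 447 1:1 pairs and zero within-pair correlation (both assumptions; the plan matches 1:3), the base is s = 0.2904 × 0.637 + 0.363 × 0.7096 = 0.4426 and power 63.7%. At f = 5%, type I error is 3.8% for g = 25% and power is 48.5% for g = 60%. Only the direction of the shifts matters here, and it agrees with step 3.

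**5. Codes.** Table 2a lists 5925001500E430, 5925001500E440, 5925001500G230 and 5925001500G240 for Abilify Maintena. Table 2b lists 59250015001920 and 59250015001930. None of the four is among the 22 codes of Table 2b, so 4 of the 6 listed codes are classed as non-LAI only. Programmed literally, a claim with one of them could qualify a control, set its index date and escape the exclusion.

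**The case against.** **The size is unknown.** Neither f nor g is in the documents, and mild values do little: at f = 1% and g = 60%, power is 79.7%, about the planned 80%. If removed controls are at high risk, the rule makes a false claim for MyCite less likely. All of this stands. The table illustrates and does not estimate, and the fault is that the plan leaves the effect to chance.

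**The arms may differ less in practice.** MyCite patients can be withdrawn at the physician's or patient's request, only Day 180 completers are analysed, and 30% dropout is planned. Some LAI starters would leave that way, so f is really a difference between arms. This stands as a limit on size. Neither mechanism is an LAI rule, so the selection remains different in kind.

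**Part of the text is redacted.** Parts of SAP 3.4 and nearly all of Protocol 3.5.4 are hidden, so an unseen counterpart rule cannot be excluded. That is why the point is put as no stated counterpart. A hidden covariate in the propensity model would not help, because that score is pre-index by definition.

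**The text overrides the code list.** SAP 3.4 excludes LAIs in words, so the four codes do harm only if Table 2a is followed against it. That is fair. This part is a list error to reconcile and adds nothing to the severity.

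**Nothing is left to analyse.** SAP 5.0 records that the study ended after two patients without an efficacy assessment. This is correct and limits the point to the plan as written.

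**Conclusion.** The concern holds. On the visible text, controls are selected partly on treatment received after index, MyCite patients are not subject to a stated equivalent, and the planned matching cannot repair it. This is a rule that is wrong as written, not a missing detail.

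Its size and direction cannot be settled from the documents. Under the assumptions shown, removing 2% to 5% of controls moves one-sided type I error from 2.5% to between 3.1% and 4.2% if those removed have a 25% risk, or moves power from 82% to between 77% and 67% if they have a 60% risk. At average risk there is no effect. If the 36.3% design rate already reflects such a screen, the power figures do not apply. The code conflict is certain as a matter of text; how many patients it would touch is unknown.

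The rule should be corrected. Confidence is medium, because of the redactions and the unknown size. No reported result is affected.

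**What to change.** In SAP 3.4, define the control LAI exclusion over a fixed look-back ending at the index date, and state that LAI claims after index do not exclude a control. LAI starts after baseline or index are then treated alike in both arms. The 180 days of pre-index enrollment already required can supply the look-back. In Appendix F, move the four Abilify Maintena codes from Table 2a to Table 2b, in line with footnote 14.

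The cost is SAP wording, a code-list correction and minor reprogramming of the control pool, with no new data. One drawback should be acknowledged: 180 days of claims is only a proxy for current LAI use. It may drop controls who had already stopped, while comparable MyCite patients remain eligible. The choice of length should be justified in the SAP. The pregnancy and coverage rules for controls are outside this point.

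### The diagnosis strata used for matching are defined one way for MyCite patients (eCRF) and another way for controls (evidently claims, with a hierarchy), so matched strata need not contain like patients

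*SAP*

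**What the plan says.** SAP 3.4 (Virtual Matched Control Group) stratifies both the MyCite cohort and the pool of potential controls by schizophrenia (SCH), bipolar 1 disorder (BP1) or major depressive disorder (MDD) before matching.

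- **MyCite patients:** "The Abilify MyCite cohort psychiatric diagnosis will be based on the psychiatric diagnosis recorded in the eCRF". Protocol 3.3.4 asks for a present-day condition: "Patients must have a current diagnosis of SCH, BP1, or MDD".
- **Controls:** "The potential controls psychiatric diagnosis will be based on the psychiatric diagnosis identified", followed by a redacted source. To enter the pool a control needs "≥ 1 claim for SCH, BP1, or MDD on or before index date", and SAP Appendix F Table 1 lists ICD-10 codes for the three conditions.
- **Several diagnoses:** "the following hierarchy will be applied to potential controls: SCH>BP1>MDD". No readable text gives a rule for a MyCite patient with more than one of these diagnoses.
- **Use of the strata:** "logistic regression will be used within each psychiatric diagnosis to estimate a propensity score for each patient", and matching follows from those scores.
- **Check before outcomes:** an overlap plot, and "comparing balance in all baseline characteristics across the cohorts via standardized mean differences", with absolute values above 10% flagged for possible investigation or regression adjustment.

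**The concern.** SAP 3.3 marks randomization as not applicable, so matching is the main protection for the primary comparison. Matching within strata helps only if the stratum label means the same thing in both arms. Here it differs in its source (physician record versus, evidently, claims) and in its handling of multiple diagnoses (an upward hierarchy for controls, nothing stated for MyCite patients). It may also differ in timing: current diagnosis in one arm, possibly any past claim in the other.

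Take a person whose treating physician now records MDD and whose claims also contain a schizophrenia diagnosis that the control rule would pick up. As a MyCite patient this person is in the MDD stratum. As a control the same person is in the SCH stratum. The MyCite patient is then scored and matched against MDD controls from whom that history has been removed. If such people have a different 180-day hospitalization risk from the rest of the stratum, the primary difference is biased.

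**Working it through.** **1. Is the control source claims?** The name is redacted. The pool criterion is written in terms of claims and Appendix F supplies diagnosis codes, so claims is a fair inference. The asymmetry does not depend on it, because the eCRF source for one arm and the controls-only hierarchy are both readable.

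**2. Who is affected?** A control with a single qualifying diagnosis is not moved by the hierarchy. The problem lies with people who have more than one of the three diagnoses, or whose eCRF and claims labels disagree. The documents do not say how many there are.

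**3. Would the planned checks show it?** Not on diagnosis itself: it is the stratifying label, so it agrees within every matched set. The problem would show only through correlated covariates such as comorbidities, psychiatrist visits or antipsychotic fills.

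**4. The plan's own figures.** SAP 4.2 gives 29.04% versus 36.30% (difference 7.26 points), 1:3 matching, 80% power, significance level 0.025, unpooled Z-test and 447 MyCite patients. With (1.960 + 0.842)² = 7.849:

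- As stated: 7.849 × [0.2904 × 0.7096 + (0.363 × 0.637)/3] / 0.0726² = 422.
- With the division by 3 applied to the MyCite variance instead: 7.849 × [0.363 × 0.637 + (0.2904 × 0.7096)/3] / 0.0726² = 446.6, that is 447.

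The second form reproduces 447. It exceeds 422, so the discrepancy is on the safe side, and it is separate from this point. I use 447 and 3 × 447 = 1341. The standard error is √(0.2061/447 + 0.2312/1341) = 0.02517, and power at the planned effect is Φ(0.0726/0.02517 − 1.960) = 82%.

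**5. Illustration of size (assumed inputs).** The documents give neither event rates by diagnosis nor a misclassification rate. Assume:

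- SCH 45%, BP1 40%, MDD 30%. With the plan's 25/25/50 mix: 0.25 × 45 + 0.25 × 40 + 0.50 × 30 = 36.25%, consistent with 36.3%.
- A share x of each stratum is cross-classified: present in the MyCite MDD stratum but, among controls, placed in SCH or BP1.
- These patients have one common risk r.
- Covariates recover none of the difference.

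With no treatment effect, the MyCite rate exceeds the control rate by x(r − 0.30) in MDD, x(0.45 − r) in SCH and x(0.40 − r) in BP1. Weighted:

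0.50x(r − 0.30) + 0.25x(0.45 − r) + 0.25x(0.40 − r) = 0.0625x.

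The risk r cancels. Power is Φ((0.0726 − 0.0625x)/0.02517 − 1.960).

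| x | Bias against MyCite (points) | Share of 7.26 | Power |
|---|---|---|---|
| 10% | 0.6 | 9% | 75% |
| 20% | 1.25 | 17% | 67% |
| 30% | 1.9 | 26% | 57% |

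**6. Direction.** In general terms the bias is 0.5x × [(SCH rate + BP1 rate)/2 − MDD rate]. Its sign depends on the assumed ordering of the rates. If the MDD rate exceeded the average of the other two, the bias would favour MyCite. For a net bias of +1.0, +2.0 or +3.0 points in that direction, with 36.3% in both arms and standard error √[0.2312 × (1/447 + 1/1341)] = 0.02626, the true one-sided type I error is Φ(bias/0.02626 − 1.960) = 0.057, 0.115 or 0.207 instead of 0.025.

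**The case against.** **The plan has some protection.** The propensity model may include comorbidities, psychiatrist visits, antipsychotic fills and a redacted covariate. Imbalance above 10% can lead to regression adjustment, and the models are fixed before outcomes are seen. This stands in part. A reader might infer that the mislabelling cannot be repaired once the strata are formed; the documents do not support that, because these covariates could recover some of it. But none of them is certain to be in the model, and no readable text plans a comparison of eCRF and claims diagnoses.

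**The stratum rule is partly redacted.** The any-time claim criterion governs entry to the pool; the look-back used to assign the stratum is not visible. This stands. Whether one old schizophrenia claim would move a control cannot be confirmed.

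**A larger bias is tempting but inconsistent.** A reader might give cross-classified patients SCH/BP1 risk (42.5%) in the MyCite MDD stratum and MDD risk (30%) in the control SCH and BP1 strata. That yields 0.125x, or 1.25, 2.5 and 3.75 points. It assigns two risks to one type of patient; with a single risk the figure halves.

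**Not every stratum need shift.** With r = 0.30 the MDD stratum does not move, and with r = 0.425 the BP1 shift changes sign. This stands.

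**A common look-back may not exist.** Controls need at least 180 days of enrolment before index; no readable text requires this of MyCite patients, who need only be actively enrolled. This stands, and the fix needs a fallback.

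**Conclusion.** The asymmetry is explicit in SAP 3.4. Following the plan exactly can place people with identical multi-diagnosis histories in different strata because of their arm. What the documents establish is that matched strata need not contain like patients. A reader might go further and conclude that the strata do not contain like patients, or that the primary result is biased in a known direction. The text does not support either: single-diagnosis controls are untouched by the hierarchy, and neither the amount of cross-classification nor the risks by diagnosis are given.

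The 0.6 to 1.9 points rest wholly on the assumed 45/40/30% rates, x between 10% and 30%, one common risk and no recovery through covariates. On those assumptions the harm is lost power; on others it is inflated type I error. The power figures use the sizing Z-test, not the McNemar test in SAP 4.4.

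The plan should be changed on this point if the design is reused. SAP 5.0 records that the study stopped after two patients with no efficacy assessment, so no reported result is affected.

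**What to change.** In SAP 3.4, assign the matching stratum in both arms with the same claims algorithm: same codes, same look-back, same hierarchy. This looks feasible because Protocol 3.3.4 requires that "Patients are actively enrolled in an Anthem-affiliated commercial, Medicaid, or Medicare health plan with medical and pharmacy benefits". In addition:

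- State the fallback: use the eCRF diagnosis for MyCite patients with no qualifying claim or too little prior enrolment, and report how many there are.
- Tabulate agreement between eCRF and claims diagnoses in the MyCite arm before outcomes are assessed.
- Keep the eCRF-based strata as a sensitivity analysis of the primary endpoint.
- Align the Appendix F Table 1 group labels (Depression, Bipolar disorder) with MDD and BP1, or say that the broader groups are intended.

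The cost is SAP wording and some programming. The fallback leaves a small residual asymmetry. Claims-based strata may differ somewhat from the enrolled diagnosis mix, so the 25% enrolment minimums should stay on the eCRF diagnosis. The planned 447, 640 and approximately 1350 do not change.
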